9 CLINICAL MONITORING

Clinical site monitoring is conducted to ensure:

- that the rights of the participants are protected;
- that the study is implemented per the approved protocol, Good Clinical Practice and standard operating procedures; and,
- the quality and integrity of study data and data collection methods are maintained.

Monitoring for this study will be performed by NCI CCR Office of Sponsor and Regulatory Oversight (OSRO) and Regulatory Oversight Support (SROS) Services contractor. Clinical site monitoring activities will be based on OSRO standards, FDA Guidance E6(R2) Good Clinical Practice: Integrated Addendum to ICH E6(R1) March 2018, and applicable regulatory requirements.

Details of clinical site monitoring will be documented in a Clinical Monitoring Plan (CMP) developed by OSRO. CMPs will be protocol-specific, risk-based and tailored to address human subject protections and integrity of the study data. OSRO will determine the intensity and frequency of monitoring based on several factors, including study type, phase, risk, complexity, expected enrollment rate, and any unique attributes of the study and the site. The Sponsor will conduct a periodic review of the CMP to confirm the plan's continued appropriateness. A change to the protocol, significant or pervasive non-compliance with GCP, or the protocol may trigger CMP updates.

OSRO SROS Monitoring visits and related activities will be conducted throughout the life cycle of each protocol. The first activity is before the study starts to conduct a Site Assessment Visit (SAV) (as warranted), followed by a Site Initiation Visit (SIV), Interim Monitoring Visit(s) (IMVs), and a study Close-Out Visit (COV).

Some monitoring activities may be performed remotely, while others will occur at the study site(s). Monitoring visit reports will describe visit activities, observations, and associated action items or follow-up required for resolution of any issues, discrepancies, or deviations. Monitoring

reports will be distributed to the study PI, NCI CCR QA, CCR Protocol Support Office, coordinating center (if applicable), and the Sponsor regulatory file.

The site Monitor will inform the study team of any deviations observed during monitoring visits. If unresolved, the Monitor will request that the site Staff enter the deviations in the CCR Protocol Deviation Tracking System (PDTs) for deviation reporting to the Sponsor and as applicable per institutional and IRB guidance.

10 STATISTICAL CONSIDERATIONS

- Phase I: To determine the MTD/ recommended Phase 2 dose (RP2D) of EP0057 in combination with olaparib in patients with refractory cancers
- Phase II: To determine the antitumor activity of olaparib plus EP0057 with respect to progression free survival at 16 weeks in SCLC patients with resistant or sensitive relapse
- Expansion: To determine overall response rate of EP0057 plus olaparib in patients with mCRPC and urothelial carcinoma

10.1 PHASE I AND PHASE II

For the phase I portion of the trial, a standard 3+3 design will be used, to determine the RP2D/MTD of EP0057 in combination with olaparib. The theoretical maximum number of subjects required to determine the MTD in the phase I portion of the study is 30 subjects (6 per dose level), although it is expected that as few as 15 subjects in 4 dose levels would be required to reach an MTD.

Sensitivity to first-line chemotherapy has been considered as the main driver of second-line therapy outcome in SCLC. For this reason, relapsed SCLC has been traditionally classified into sensitive and resistant disease according to the type of response to first-line therapy and to treatment-free interval (treatment-free interval longer or shorter than 60–90 days) (68). Although this definition was derived many years ago and based on a small patient series (69), first-line chemotherapy sensitivity has since been confirmed to be a prognostic factor to predict response to second line and further therapy in meta-analyses (3) and randomized studies (70, 71).

Published results suggest that the median PFS for single agent therapy with topotecan (currently the only approved second line therapy) for previously treated patients which included a combination of sensitive and resistant /refractory SCLC patients was approximately 3 months (median 3.0-4.3 months for sensitive and 1.5-2.6 months for refractory; (68, 70-73) (refer to **Table 15**).

A recent randomized study of PARP inhibitor plus chemotherapy in relapsed SCLC patients (both platinum-sensitive and resistant patients were included) found no significant difference in 4-month PFS between temozolomide/veliparib (20 of 55; 36%) and temozolomide /placebo (13 of 49; 27%; $P = .19$) (74). Median PFS was 3.8 months and 2.0 months in the temozolomide /veliparib and temozolomide /placebo arms, respectively (log-rank $P = .39$; hazard ratio, 0.84; 95% CI, 0.56 to 1.25).

Patients with both sensitive and resistant SCLC will be enrolled in the phase II study and analyzed together. The phase II trial will be conducted using an optimal two-stage design in order to rule out an unacceptably low success rate of 25% ($p_0=0.25$) in favor of an improved success rate of 45% ($p_1=0.45$). With alpha=0.10 (probability of accepting a poor treatment=0.10)

and beta = 0.20 (probability of rejecting a good treatment=0.20), this first stage will enroll 15 evaluable patients, and if 0 to 4 of the 15 have a success (that is, 0 to 4 make it to 16 weeks without progression), then no further patients will be accrued. If 5 or more of the first 15 patients have success, then accrual would continue until a total of 27 evaluable resistant/refractory patients have been enrolled. As it may take up to 4 months to determine if a patient has experienced a success at 16 weeks, a temporary pause in the accrual may be necessary to ensure that enrollment to the second stage is warranted. If there are 5 to 9 patients with a success out of 27 patients, this would be an uninterestingly low success rate. If there were 10 or more of 27 (37%) who experienced a success, this would be sufficiently interesting to warrant further study in later trials. Under the null hypothesis (25% success rate), the probability of early termination is 68.7%.

Patients who receive at least one dose of the study drug will be evaluable for safety. Patients who complete at least one cycle of treatment and have a follow up imaging study will be evaluable for efficacy. The maximum number of patients on the phase I portion of the trial is 30 and phase II SCLC may accrue up to 27 evaluable patients. Thus, the maximum number of evaluable patients which may enroll on the phase I and II cohorts is 57. In order to allow for a small number of in-evaluable patients, the accrual ceiling will be set at 60 for these cohorts. It is anticipated that approximately 1 to 2 patients per month may enroll onto these cohorts.

Table 15. Selected randomized studies of cytotoxic agents for SCLC

No.	Patients	Treatment s	Primary endpoint	Median PFS-topotecan	Median OS-topotecan	Reference
1	Sensitive SCLC	Topotecan (N=107) vs. CAV (N=104)	ORR	3.3 months (sensitive)	6.3 months (sensitive)	(68)
2	Refractory or sensitive SCLC; 2 nd line	Topotecan (N=213) vs. amrubicin (N=424)	OS	4.3 months (sensitive) 2.6 months (refractory)	9.9 months (sensitive) 5.7 months (refractory)	(71)
3	Sensitive SCLC 2:1	Topotecan (N=26) vs. amrubicin (N=50)	ORR	3.3 months (sensitive)	7.6 months (sensitive)	(73)
4	Refractory or sensitive SCLC	Topotecan (N=30) vs. amrubicin (N=29)	ORR	3.0 months (sensitive) 1.5 months (refractory)	NA	(70)
5	Sensitive SCLC; 2 nd line	PO (N=153) vs. IV	ORR	3.7 months (sensitive)	8.7 months (sensitive)	(72)

No.	Patients	Treatment s	Primary endpoint	Median PFS-topotecan	Median OS-topotecan	Reference
		(N=151) topotecan				

10.2 PHASE II EXPANSION COHORTS

10.2.1 Expansion Cohort (Urothelial Carcinoma)

The primary objective of this cohort is to determine the clinical response rate to EP0057 and olaparib in patients with bladder cancer. Data from a single trial of 310 patients with metastatic bladder cancer receiving atezolizumb alone demonstrated an ORR of 15%. To establish at least slightly improved efficacy of this treatment combination compared to single agent atezolizumab, the primary objective would be to determine if using the proposed agents would rule out a 10% response rate and result in a response rate consistent with 25%. As such, this cohort of the trial will be conducted using a Simon optimal two-stage phase II trial design (75) to rule out an unacceptably low PR+CR rate of 10% ($p_0=0.10$) in favor of an improved response rate of 25% ($p_1=0.25$). With alpha=0.10 (probability of accepting a poor treatment=0.15) and beta = 0.20 (probability of rejecting a good treatment=0.20), the first stage will enroll 13 evaluable patients, and if 0 to 1 of the 13 have a clinical response, then no further patients will be accrued in this cohort. If 2 or more of the first 13 patients have a response, then accrual would continue until a total of 34 evaluable patients have been treated. As it may take up to several months to determine if a patient has experienced a response, a temporary pause in the accrual may be necessary to ensure that enrollment to the second stage is warranted. If there are 2 to 5 patients with a response out of 34 patients, this would be an uninterestingly low response rate. If there were 6 or more of 34 (17.6%) who experienced a response, this would be sufficiently interesting to warrant further study in later trials. Under the null hypothesis (10% response rate), the probability of early termination is 62.1%.

It is expected that approximately 1 to 2 patients per month may enroll onto this cohort in the trial. Thus, it is expected that 2 to 3 years may be required to enroll up to 34 evaluable patients. To allow for a small number of inevaluable patients, the accrual ceiling for this cohort will be set at 36 patients. Analysis of correlative studies will be exploratory.

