1 INTRODUCTION

1.1 STUDY OBJECTIVES

1.1.1 Primary Objectives

- 1.1.1.1 Phase I: To determine the MTD/recommended Phase 2 dose (RP2D) of EP0057 plus olaparib in patients with refractory cancers.
- 1.1.1.2 Phase II: To determine the antitumor activity of olaparib plus EP0057 with respect to progression free survival 16 weeks in SCLC patients with resistant or sensitive relapse
- 1.1.1.3 Phase II Expansion Cohorts: To determine overall response rate of EP0057 plus olaparib in patients with mCRPC and urothelial carcinoma

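### Urothelial cohort: the stated aim is improvement over atezolizumab (15% ORR), but the 6-of-34 rule controls error only against 10%, and alpha = 0.10 is glossed as 0.15

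*Combined protocol and SAP*

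**What the plan says.** Section 10.2.1 begins with a non-comparative objective: "The primary objective of this cohort is to determine the clinical response rate to EP0057 and olaparib in patients with bladder cancer". It then cites a single trial of 310 patients in which atezolizumab alone gave an ORR of 15%. Section 1.2.2 gives the figure as 14.8%, with a 95% CI of 11.1 to 19.3. The next sentence opens "To establish at least slightly improved efficacy of this treatment combination compared to single agent atezolizumab" and goes on to say that "the primary objective would be to determine if using the proposed agents would rule out a 10% response rate" and give a rate consistent with 25%.

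The design is a Simon optimal two-stage with p0 = 0.10 and p1 = 0.25. Accrual stops with 0 or 1 response in 13 patients and otherwise continues to 34. The final rule is "6 or more of 34 (17.6%) who experienced a response, this would be sufficiently interesting to warrant further study in later trials". The error rates are given as "With alpha=0.10 (probability of accepting a poor treatment=0.15) and beta = 0.20".

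The formal objectives make no comparison. Section 1.1.1 has "To determine overall response rate of EP0057 plus olaparib in patients with mCRPC and urothelial carcinoma", and the opening of section 10 repeats it. The matching SCLC sentence in section 10.1 reads "With alpha=0.10 (probability of accepting a poor treatment=0.10". Section 1.2.18 records that accrual to the urothelial cohort has been closed.

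**The concern.** There are two faults of unequal weight.

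1. **Aim and test do not match.** The comparator is put at 15%, the aim is to establish something better than it, and the test rejects only 10%. No reason is given for a null below the cited comparator, and no threshold or analysis against 15% is set for this cohort. The cut-off of 6 of 34 is 17.6%, numerically above 15%, so a reader could take a bare pass as meeting the atezolizumab aim. The clause also departs from the non-comparative objectives in sections 1.1.1 and 10 and in the first sentence of 10.2.1 itself.

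2. **The gloss on alpha contradicts alpha.** For this design, the probability of accepting a poor treatment is alpha. One sentence gives it as both 0.10 and 0.15, so the error rate of the design is misstated in the text that governs it.

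At stake is what may be claimed for a primary endpoint of the trial. No enrollment or stopping decision turns on it.

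**Working it through.** **Inputs, all from section 10.2.1:** n1 = 13, stop at 1 or fewer; N = 34, go at 6 or more; p0 = 0.10, p1 = 0.25, alpha = 0.10, beta = 0.20; comparator ORR 15%.

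**Formulas.** With X1 ~ Bin(13, p) and X2 ~ Bin(21, p):

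- PET(p) = P(X1 ≤ 1) = (1−p)^13 + 13p(1−p)^12
- P(k or more of 34; p) = Σ over x = 2 to 13 of P(X1 = x) · P(X2 ≥ k − x)

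**Step 1: reproduce the plan.** PET(0.10) = 0.2542 + 0.3672 = 0.6213, the stated 62.1%. P(6 or more) is 0.0957 at 10% and 0.8108 at 25%, so alpha ≤ 0.10 and power ≥ 0.80 both hold. A search for the Simon optimal design at these inputs returns 1/13, 5/34, which is the plan's design.

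**Step 2: the same rule at the comparator's rate.** PET(0.15) = 0.1209 + 0.2774 = 0.3983.

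| True ORR | P(6 or more of 34) | P(9 or more of 34) | P(6 to 8 of 34) |
|---|---|---|---|
| 10% | 0.0957 | 0.0049 | 0.0957 − 0.0049 = 0.0908 |
| 15% | 0.3379 | 0.0561 | 0.3379 − 0.0561 = 0.2818 |
| 25% | 0.8108 | 0.4719 | 0.8108 − 0.4719 = 0.3389 |

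At 14.8% the pass probability is 0.3265. The 33.8% at 15% is a pass probability at a rate between p0 and p1. It is not a breach of the type I error, which is defined at 10%.

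**Step 3: what each passing count excludes.** Limits are stage-adjusted, with outcomes ordered by stage and then by responses. For k of 34, the 80% lower limit solves P(k or more; p) = 0.10 and the upper limit solves 1 − P(k+1 or more; p) = 0.10. The lower limit is therefore a one-sided 90% bound, matching the trial's 10% level.

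| Responses | 80% interval | 15% excluded? |
|---|---|---|
| 6/34 | 10.1–30.9% | no |
| 7/34 | 12.2–33.3% | no |
| 8/34 | 14.5–36.0% | no |
| 9/34 | 16.8–38.9% | yes |

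With 95% intervals, 6/34 gives 7.1–37.9%, 9/34 gives 13.0–44.9% and 10/34 gives 15.2–47.7%, so 15% is excluded only from 10.

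**Step 4: which alpha the boundaries belong to.** With p0 = 0.10, p1 = 0.25 and beta = 0.20, the optimal design at alpha = 0.10 is 1/13, 5/34 (attained 0.0957, power 0.811). At alpha = 0.15 it is 1/16, 3/21 (attained 0.149, power 0.803). The plan's boundaries are those for 0.10.

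**Step 5: the cost of testing 15% instead.** The Simon optimal design for 15% against 25% at alpha = 0.10 and beta = 0.20 (N searched to 110) is 4/29, 16/84, with attained error 0.0992 and power 0.806. That is up to 84 patients, against 34.

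**The case against.** The strongest reply is that the sentence defines its own operational objective: it goes on to name 10% as the rate to rule out and 25% as the target. The atezolizumab clause then reads as rationale. An uninteresting rate below the historical figure with a target above it is a coherent screening design, and the go rule claims only that further study is warranted. This stands as a defense of the design and is why no boundary need change. It does not rescue the clause. The clause speaks of establishing improvement over a named comparator, and nothing in the section disclaims that reading for a bare pass.

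A second reply is that accrual has closed, for slow accrual and competing protocols. If 34 was not reached, the final rule never applies. This limits the practical weight. The documents do not give the number accrued, and the section still governs how a primary endpoint is read.

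Third, 15% is itself an estimate (95% CI 11.1 to 19.3 in section 1.2.2). The 9/34 lower limit of 16.8% is below 19.3%, so even 9 responses would not settle a cross-trial comparison. That is right, and it is a reason not to adopt 9 of 34 as a new threshold.

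Finally, section 10.2.1 specifies no interval for this cohort, and the choice between adjusted and ordinary limits matters little. For an assumed 4 responses in 24 after passing stage 1, the 80% limits are 8.1–31.9% adjusted and 7.5–30.6% ordinary. The interval advice is therefore secondary.

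**Conclusion.** The concern holds on both counts. Meeting the 6-of-34 rule supports ruling out 10% and going on to further study; it does not by itself support improvement over atezolizumab. Counts of 6 to 8 pass the rule while remaining compatible with 15%. The chance of such a result is 28.2% if the true ORR is 15% and 33.9% if it is 25%. The 0.15 gloss is wrong as written: the attained error at 10% is 0.0957, the boundaries are the alpha = 0.10 optimum, and the SCLC text has 0.10 in both places. The gloss is a one-number slip and adds little weight.

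The figures assume the two-stage rule is followed as written with 34 evaluable patients, and treat 15% as a fixed benchmark. The point should be corrected, but its reach is confined to the stated claim and its reporting.

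**What to change.** In section 10.2.1:

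- State the aim as ruling out a 10% response rate in favor of 25%.
- Add that meeting the 6-of-34 cut-off is not evidence of improvement over atezolizumab.
- Change 0.15 to 0.10 in the explanation of alpha.

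Secondary, for reporting only: if the ORR is given with an interval, use a two-stage-adjusted one whenever the cohort continued past the 13-patient look, including if it closed between 13 and 34. Use an ordinary exact interval if it ended at or before 13. Do not apply the 34-patient cut-off if 34 was not reached.

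The cost is an edit to one section, a weaker stated claim for the cohort and a short extra calculation for the interval. No patients are added and no boundary changes. Redesigning to test 15% would be out of proportion.

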10.2.2 Expansion Cohort (mCRPC)

The primary objective of this exploratory cohort is to determine the clinical response rate to EP0057 and olaparib in patients with prostate cancer who are identified as having one of several possible genetic mutations.

In a published study of 16 patients with prostate cancer who have one of a set of specified mutations, 14 (87.5%) had experienced a clinical response when treated with olaparib alone. While it is unlikely that this could be improved upon, it would be of interest to explore if a similarly high response rate could be seen in patients treated at the NCI with EP0057 and olaparib.

Patients with prostate cancer will be enrolled onto this cohort and biopsied, and the patients who are found to have any of a set of defined genetic mutations (in the DNA damage repair pathways), will receive EP0057 and olaparib and be evaluated for clinical response by PSA and RECIST criteria. It is anticipated that 25-30% of patients will be found to possess one of the

mutations of interest. To obtain at least 5 patients who could be evaluated for response, 25 total patients will undergo procedures necessary to determine if they possess the appropriate mutations. If the true probability of a mutation were 30%, then with 25 patients, there is a 91.0% probability of identifying 5 or more with mutations, including a 32.3% probability of identifying 9 or more patients with mutations. If the true probability of a mutation were 25%, with 25 patients, there is a 78.6% probability of identifying 5 or more with mutations, and a 14.9% probability of obtaining 9 or more with mutations. Thus, by enrolling 25 patients, there should be between 79% and 91% probability of identifying 5 or more patients with mutations, and between 15% and 32% probability of potentially identifying 9 or more with mutations.

For however many patients are identified with mutations, expected to be between 5 and 9 out of 25, these patients will receive treatment with EP0057 and olaparib, and will have their responses evaluated using PSA and RECIST criteria. The fraction with responses obtained will be reported along with 80% and 95% two-sided confidence intervals, and the results compared, at least informally, to those from the published study with similar patients treated with olaparib alone. While the actual number of these patients to receive EP0057 and olaparib is likely to be between 5 and 9, the trial will continue to enroll and evaluate up to the ceiling of 25 patients with prostate cancer, unless an early stopping rule is invoked. If among the first 5 treated patients with prostate cancer who have DNA damage repair pathway mutations, only 1 of 5 responds, then no further patients will be enrolled since the upper one-sided 90% CI bound on $1/5 = 58.4\%$, which would be below the lower one-sided 90% CI bound on $14/16$ from the published study (70.0%), and thus be inconsistent with the prior results.

The remaining patients without a mutation in their DNA damage repair pathway will also receive the combination of EP0057 and olaparib. It is expected that out of 25 evaluable patients enrolled on the trial, between 16 and 20 will not have these mutations. For these patients, it would be desirable to determine if their response rate would exceed 5% and be consistent with 25% or greater. Using that as a guideline, if there are 16 patients without the proper mutations who receive the combination treatment, 3 responses in 16 would be associated with a two-sided 80% exact confidence interval of 7.1-37.1%, and 4 responses in 16 would be associated with a two-sided 80% exact confidence interval of 11.4 to 43.9%. With 20 patients without the proper mutations, 3 responses in 20 is associated with the same confidence interval of 5.6 to 30.4%, and 4 responses in 20 would have a confidence interval of 9.0-36.1%. The values for 17 to 19 patients have similar confidence intervals. Thus, in the expected range of 16 to 20 patients without mutations, a minimum of 3 responses, but preferably 4 or more, would be the lowest numbers of responses obtained which could be considered sufficiently interesting to allow the treatment to be evaluated further in these patients. As these patients are being accrued and treated while aiming to attain the greatest number of patients with the DNA damage repair pathway mutations, there will be no early stopping rule based on poor response in this group of 16 to 20 patients.

It is expected that approximately 1 patient per month may enroll onto this cohort in the trial. Thus, it is expected that 2 years may be required in order to enroll up to 25 evaluable patients. To allow for a small number of inevaluable patients, the accrual ceiling for this cohort will be set at 27 patients.

10.3 SAMPLE SIZE DETERMINATION

With up to $30+27+34+25= 116$ evaluable participants needed for the phase 1 dose escalation and expansion phases, as well as planning for a small number of inevaluable participants (10), we intend to initiate intervention in up to 126 participants. Note: To allow for screen failures (10), a total of 136 will be set for the purposes of the NIH accrual ceiling.

Overall, 1 – 2 patients per month are expected to enroll across all of the cohorts. It is expected that enrollment will be completed in 6 – 8 years.

